7.4 Analysis of serum estradiol and testosterone levels

Paired t-tests will be used to compare estradiol samples sent to the standard clinical laboratory utilized by UCSF (Quest Diagnostics) and those samples sent to a research lab in England that has reported the use of an ultrasensitive assay to detect very small changes in estradiol levels in postmenopausal women. With 35 samples we will have 90% power to detect a 0.564 sd difference between the two systems of measurements. We will also measure the correlation to assess the agreement between these two measurements. The data for one method will be plotted against the other method to determine whether the relationship between the two is linear over the range of values.

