3. STUDY PLAN AND PROCEDURES

3.1 Overall study design

This will be a single institution open label randomized Phase II study evaluating intravaginal testosterone cream vs. the Estring for vaginal dryness and/or decreased libido in early breast cancer patients treated with an aromatase inhibitor. Up to 80 early stage breast cancer patients will be enrolled over 36-48 months in order to have a total of 70 evaluable patients. To be considered evaluable, patients must complete their baseline evaluation and week 4 safety blood draw. Randomization of patients will attempt to balance the number of patients in each group based on self reported or medically documented depression, use of antidepressants, and relationship status (single vs. partnered). Patients will be randomized to a 12 week course of treatment with either:

- Testosterone Cream 1% micronized in velvachol - 0.5 gm of cream vaginally 3 times a week for total of 12 weeks of treatment
- Estring 2mg ring inserted vaginally once every 12 weeks

Patients will complete quality of life surveys including the CARES Sexual Interest and Sexual Dysfunction Subscales (Appendix A), which includes a single item sexual satisfaction measure previously tested by Ganz, at day 1 (baseline), week 4, and at the end of week 12 (the survey may be done either in the clinic, or at home and then mailed/faxed). Patients will undergo a gynecologic exam at baseline and at the end of week 12 (or sooner if they withdraw from the study or experience unexpected side effects). During this exam, the vaginal epithelium will be assessed using a 3-point scale evaluating color, petechiae, friability and dryness (Appendix B). Within each treatment group, composite scores of the vaginal epithelium at baseline will be compared to composite scores at study termination.

Serum estradiol assays sent to the UCSF clinical laboratory are sent out to Quest Diagnostics, which uses extraction chromatography RIA for their ultra-sensitive estradiol. Day 1 and week 4 samples will also be stored temporarily and then sent in batches to a specialized research lab which has developed an assay to quantify low levels of estradiol found in post-menopausal women. This assay is a radioimmunoassay after ether extraction, and has a sensitivity limit of 3pmol/l. Serum testosterone levels will also be sent to Quest, which uses an ultrasensitive testosterone measurement which is run by liquid chromatography tandem mass spectrometry.

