7.3 Secondary Outcomes Statistical Analysis

A secondary outcome variable in this study is the change in the scores on the CARES Sexual Dysfunction Subscale from baseline to week 12 within each patient treatment group. The ESTRING and testosterone cream treatment groups will be analyzed independently. Another secondary outcome variable will be the difference in the change in CARES Sexual Dysfunction Subscale from baseline to week 12 between the ESTRING and testosterone cream treatment groups.

Based on results from previous studies investigating menopausal symptoms and sexual dysfunction in breast cancer survivors published by Ganz (11, 39), mean scores on the CARES Sexual Dysfunction Subscale (SDS) was 1.35 ± 1.13 for one group and 1.53 ± 1.17 for the other group (on a scale on 0-4). Within patient correlations were not published in either of these studies, but we would expect it to be 0.8 or greater. The formula for the sd when comparing 2 correlated measurements is: $\text{sd of difference} = \sqrt{2*\text{sd}^2*(1 - \text{cor})}$.

Based on a standard deviation of 1.17 from a study of different patients, a table for the $\text{sd}(\text{diff})$ as a function of the correlation is:

corr	$\text{sd}(\text{diff})$
0.7	0.91
0.8	0.74
0.9	0.52

With 35 evaluable patients in each treatment group (ESTRING and testosterone cream), we will have 90% power to detect an improvement of 0.41 when the correlation is 0.8, based on a two-sided paired t-test at 5% level of significance. This translates to a reduction from 1.53 to 1.12 for treated patients.

Using a two-sample t-test, and with 35 evaluable patients in each treatment group, we would have 80% power to detect a difference of 0.57 in the change scores (e.g. a reduction of 0.1 in one group vs. a reduction of 0.67 in the other group). Currently, there is no published research to suggest an expected effect size for these interventions. However, after carrying out this trial we will have estimates for the reduction for each treatment type and could use these estimates to plan a larger study to determine if one intervention is actually superior to the other.

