Appendix C.

APPENDIX D.: Blood Specimen Collection and Handling Instructions for Research serum estradiol assay

At baseline and Week 4, one sample will be collected for standard hormone testing at UCSF or Quest Diagnostic® labs (routine lab test), and a second sample will be collected for a specialized low-level estradiol assay (research lab test).

- The lab slip should specify that an extra sample of blood is to be collected for the study.
- At least 3-4 ml of blood is needed to create the research serum sample that will be sent for low-level estradiol assay.
- The study personnel responsible for obtaining the research sample from the lab should label the red top vacutainer tube with the patient's identification (patient number and patient initials), protocol number (067519), date and time of blood draw (dd-MMM-yyyy format for the date (i.e. 01-JAN-2003) and 24:00 hour clock format for the time).
- The **research lab sample** will be collected by the lab technician in a red top vacutainer at the time the standard hormone blood sample is collected using standard venipuncture techniques.

Serum Collection Tube:

1. 4-6 mL red top vacutainer tube

Specimen Transfer Tube:

1. Non-sterile polypropylene specimen tube (cryovial) with screw cap.
2. Freezer resistant specimen label to fit the cryovial.

Serum Collection and Shipping Instructions

1. Draw 3-4 mL of blood (yielding ≥ 0.5 mL of serum) into a red top vacutainer tube at each designated specimen timepoint using standard venipuncture techniques.
2. After collection, the study personnel will take the sample to the centrifuge.
3. Allow the blood to clot upright at room temperature for 30 minutes.
4. Centrifuge the sample for approximately 15 minutes.
5. Completely fill out the label with the corresponding patient's identification (patient ID number and patient initials), protocol number (067519), date and time of blood draw (dd-MMM-yyyy format for the date (i.e. 01-JAN-2003) and 24:00 hour clock format for the time) and affix it to one of the room temperature polypropylene specimen tubes.
 - A freezer resistant label should be used so that water or freezing temperatures do not destroy the label since samples must remain frozen until shipment

6. Draw off the supernatant and pipette 0.5mL – 1.5 mL of the serum into the properly labeled polypropylene specimen tube.

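### Section 7.4 assigns agreement between the two estradiol assays to a correlation, and nothing planned quantifies how far the assays differ on an individual sample

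*Protocol*

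**What the plan says.** Secondary objective 2 (Protocol synopsis and section 2.2) is to compare estradiol from the standard clinical laboratory with estradiol from an ultrasensitive research assay. Section 7.4 gives the analysis in three parts:

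- Paired t-tests between the two laboratories, with the power statement "With 35 samples we will have 90% power to detect a 0.564 sd difference between the two systems of measurements".
- A correlation, with its purpose stated: "We will also measure the correlation to assess the agreement between these two measurements".
- A plot, also with its purpose stated: "The data for one method will be plotted against the other method to determine whether the relationship between the two is linear".

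Section 7.4 names no limits of agreement, no concordance measure and no acceptable difference. It does not say which arm or visit the 35 samples come from.

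On the samples, section 3.1 says "Day 1 and week 4 samples will also be stored temporarily and then sent in batches to a specialized research lab". Appendix D confirms the pairing: "At baseline and Week 4, one sample will be collected for standard hormone testing", with a second tube for the research assay. Section 3.1 plans 70 evaluable patients, each of whom must have the baseline evaluation and the week 4 draw. It also says that the research assay "has a sensitivity limit of 3pmol/l", whereas the clinical values are judged in pg/ml.

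**The concern.** This is not a detail left open for a statistical analysis plan. The protocol names a statistic and gives it a task that it cannot do. Two assays can be perfectly correlated and disagree on every sample. They can also have equal means, and so pass a t-test, while differing widely from sample to sample.

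A reader of objective 2 will want to know by how much the clinical result may differ from the research result for one woman's sample. The distribution of the within-pair differences answers that question, and none of the three planned outputs reports it. At stake is a secondary objective that could be reported as good agreement on the strength of a high correlation and a non-significant t-test.

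**Working it through.** **1. The plan's own figure.** Inputs from section 7.4: n = 35 pairs, difference 0.564 sd, read as SDs of the paired difference. Section 7.4 gives no alpha or sidedness, so I take them from section 7.3: "based on a two-sided paired t-test at 5% level of significance".

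- Noncentrality = 0.564 × √35 = 3.337, df = 34, critical t = 2.032.
- Exact power = 0.8999, and the detectable difference at 90% power is 0.5641 SD. The stated figure reproduces.
- A one-sided 5% test would give 0.948 and the normal approximation 0.916. Neither matches, which supports the reading above.

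**2. What the correlation sees.** If Y = a + bX with b > 0, then r = 1 for any a and b. For Y = 2X, Lin's concordance coefficient is 2·cov/(var X + var Y + squared mean difference) = 4s²/(5s² + m²), where m and s are the mean and SD of X. For an assumed lognormal X with log-SD 0.6, s²/m² = e^0.36 − 1 = 0.433, so concordance = 4/(5 + 1/0.433) ≈ 0.55. Correlation is 1.00 on the same data.

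**3. What the paired t-test sees.** It tests whether the mean difference is zero.

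- It would very likely detect the two-fold bias: with 35 lognormal pairs and log-SD assumed between 0.6 and 1.2, simulated power is about 99% to 100%.
- It is blind to scatter: two unrelated assays with equal means were significant in 5.0% of 20,000 simulated trials of 35 pairs, which is just the alpha level.

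**4. The two together.** Illustration with assumed inputs: 35 pairs, of which 33 are unrelated readings (lognormal, median 5 pg/ml, log-SD 0.6) and two are high values (60 and 80 pg/ml) on which the assays roughly agree. Median r was 0.94, and in over 85% of runs r exceeded 0.9 with t-test p > 0.05. So a reassuring pair of statistics is possible when 33 of 35 samples show no agreement. How likely such data are in this trial cannot be told from the protocol.

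**5. Pairs available.** 70 evaluable patients × 2 visits = 140 pairs, or 70 at each visit if both arms are pooled. Two pairs from one patient are not independent. If the differences correlate within patient by 0.3 to 0.8 (assumed), the effective number is 140/1.3 ≈ 108 down to 140/1.8 ≈ 78.

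**6. Precision, in SDs of the paired difference.** The 95% CI half-width for a limit of agreement is t × √(1/n + 1.96²/(2(n − 1))).

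| Pairs | Detectable mean bias, 90% power | CI half-width of each limit |
|---|---|---|
| 35 (one arm, one visit) | 0.564 | 2.032 × 0.292 = 0.59 |
| 70 (both arms, one visit) | 0.393 | 1.995 × 0.205 = 0.41 |

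At 70 pairs the power for 0.564 SD would be 99.6%.

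**7. Units.** With the molecular weight of 272.39 in section 4.1, the research limit of 3 pmol/l is 3 × 0.27239 = 0.82 pg/ml. Differences have meaning only after both assays are put in one unit.

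**The case against.** The three parts of section 7.4 should be read together. The t-test addresses mean bias, which is one component of agreement. The correlation falls when errors cancel in the mean but scatter widely, and the plot would show both a slope of two and loose scatter. A reader might infer from the r = 1.00 example that the plan would miss a two-fold bias. It would not, as step 3 shows. What remains is that a plot read for linearity and a correlation do not put a number on individual differences.

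A reader might also infer that 35 is the wrong sample size. The protocol does not support that. The arithmetic is exact, 35 is the evaluable number per arm, and section 7.4 speaks of t-tests in the plural, so one arm at one visit fits. It is also conservative. Nor are 70 pairs assured: under section 7.2 an arm may stop after 10 patients, which would leave 10 + 35 = 45.

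A third tempting reading is that the primary safety endpoint is at risk. Section 3.1 defines that endpoint on the clinical laboratory's values. It needs a rise over baseline on two consecutive collections, whereas research samples exist only at day 1 and week 4. Objective 2 is a comparison of assays and is not set up to validate that classification.

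Finally, the log scale and the handling of values below an assay limit are details that an analysis plan commonly settles. That is fair. The choice of a correlation as the agreement measure is different, because the protocol itself has fixed it.

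**Conclusion.** The point holds in a limited form. Section 7.4 uses the correlation to assess agreement, which it cannot do. The t-test covers mean bias only, the plot covers linearity only, and no planned output quantifies the difference between assays for an individual sample.

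The conclusion about the method needs no assumption about the data. The size of any harm does: the concordance of 0.55 and the illustration in step 4 rest on assumed lognormal values. The protocol gives neither the expected distribution nor the clinical assay's detection limit.

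The power statement is correct as it stands. The figure of about 0.39 SD applies only if both arms are pooled at a visit and all 70 evaluable patients supply the research tube. The primary endpoint, the two-stage rule and the safety conclusion do not change. The weakness is confined to a secondary objective, but it is worth correcting because the correction is easy.

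**What to change.** Revise section 7.4 so that:

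- the main result is the mean difference with 95% limits of agreement and confidence intervals for the bias and for each limit, both assays in one unit. If differences grow with level, use the mean ratio and limits on the log scale;
- the analysis is done separately at day 1 and week 4, pooling both arms, so that two pairs from one patient are never treated as independent;
- values below an assay limit are treated as censored;
- the correlation and the plot are kept as description, and the words that give the correlation the task of assessing agreement are removed. A cross-tabulation of the two assays at 10 pg/ml may be added, also as description;
- the sample basis is stated. The 35-pair figure can stand for one arm at one visit. For pooled arms, restate it as about 70 pairs, detectable mean bias about 0.39 SD, and limits known to about ±0.41 SD.

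The cost is analysis wording. No extra samples, assays or visits are needed.

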2.2 Secondary Objectives

1. To document the systemic estradiol and testosterone levels at several time points in early breast cancer patients on aromatase inhibitors and being treated with intravaginal testosterone cream or the ESTRING.
2. To compare standard clinical laboratory measurements of serum estradiol with values of serum estradiol as measured by an ultrasensitive assay in a research laboratory.
3. To evaluate changes in gynecologic and sexual quality of life using validated questionnaires (the CARES Sexuality Subscales) in early stage breast cancer patients using intravaginal testosterone cream or the ESTRING for relief of vaginal dryness and/or decreased libido related to aromatase inhibitor therapy.

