The primary outcome variable in this study is the number of breast cancer patients being treated with either intravaginal testosterone cream or the ESTRING for a 12 week period who are found to have a persistently elevated serum estradiol level outside the post-menopausal range as defined by:

1. An elevation of serum estradiol outside of the post-menopausal range and at least 10 pg/ml higher than the baseline value on two consecutive collections at least four weeks apart.
The post-menopausal range at UCSF is ≤ 10 pg/ml (as measured by Quest Diagnostics, the lab utilized by the UCSF clinical laboratory).

2. If a patient's baseline (day 1) serum estradiol level is >10 pg/ml, the subsequent levels must be >10 pg/ml higher than the baseline value to be considered a significant elevation outside the post-menopausal range.

A secondary outcome variable is the change in scores on the CARES Sexual Dysfunction Subscale from baseline to week 12. The ESTRING and testosterone cream treatment groups will be analyzed independently.

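### Section 7.4 uses the correlation to judge agreement between the two estradiol assays, which it does not measure, and nothing else planned shows how far paired readings differ in pg/ml

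*Protocol*

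**What the plan says.** Protocol section 2.2 sets secondary objective 2: "To compare standard clinical laboratory measurements of serum estradiol with values of serum estradiol as measured by an ultrasensitive assay in a research laboratory". Section 3.1 sends Day 1 and week 4 samples to both laboratories.

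Section 7.4 plans three outputs:

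- A test of the mean difference: "Paired t-tests will be used to compare estradiol samples sent to the standard clinical laboratory" and those sent to the research laboratory. Its power statement is "With 35 samples we will have 90% power to detect a 0.564 sd difference between the two systems of measurements".
- The agreement measure: "We will also measure the correlation to assess the agreement between these two measurements".
- A plot: "The data for one method will be plotted against the other method to determine whether the relationship between the two is linear".

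The section states no acceptable difference in pg/ml, no correlation value that would count as agreement, and no SD or expected correlation for either assay. For context, section 3.1 says "The post-menopausal range at UCSF is ≤ 10 pg/ml", as measured by the clinical laboratory.

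**The concern.** The protocol gives a named statistic a purpose that it cannot serve, so this is a stated method and not a detail left open. A correlation of 1 is compatible with any constant shift and any positive change of scale. For a fixed measurement error, the correlation also depends on how much the women differ from one another, so a high value may reflect a wide sample and not close agreement.

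The other two outputs do not fill the gap. The t-test concerns the mean difference only, and two assays that differ in scale can still lie on a perfectly straight line. Objective 2 could therefore be reported with a high correlation, a non-significant t-test and a straight plot, without any statement of how far two readings of one sample lie apart. At levels near a 10 pg/ml limit, a difference of several pg/ml is what a reader of that comparison would want to know.

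**Working it through.** **1. The plan's own figure.** Inputs from section 7.4: n = 35 and a difference of 0.564 SD of the paired differences. Section 7.4 gives no alpha, so I took it from section 7.3 ("based on a two-sided paired t-test at 5% level of significance"). The noncentrality is 0.564 × √35 = 3.34 on 34 degrees of freedom. The noncentral t gives power of 89.99%, against the stated 90%. The figure reproduces, but it concerns the mean difference only.

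**2. Correlation and spread.** With between-woman SD s and the same error SD e on each assay, r = s²/(s² + e²). Assume e = 0.15 on the log10 scale:

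- s = 0.1: r = 0.0100/(0.0100 + 0.0225) = 0.31
- s = 0.4: r = 0.1600/(0.1600 + 0.0225) = 0.88

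The assay error is identical in both lines.

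**3. What the t-test catches.** A constant offset of 9 pg/ml is detected with power of essentially 100% for assay SDs of 2 to 10 pg/ml and r of 0.8 to 0.9. That kind of disagreement does not escape.

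**4. What escapes: random scatter.** Section 7.3 gives the SD of a paired difference as √(2 × sd² × (1 − cor)). It is given there for CARES scores, and I apply it here to the assays. With equal SDs and zero mean bias, the 95% limits of agreement are ±1.96 × sd × √(2(1 − r)).

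The protocol gives no SD for either assay. The only spread of serum estradiol I used is the 5 to 22 pg/ml range in section 4.1.1, from 14 postmenopausal women not stated to be on aromatase inhibitors. The expected range of 14 normal values is about 3.41 SD, so SD ≈ (22 − 5)/3.41 ≈ 5 pg/ml. This is an assumption, and the table shows values on either side of it.

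| Assumed SD (pg/ml) | r = 0.9 | r = 0.8 | r = 0.7 | r = 0.5 |
|---|---|---|---|---|
| 2 | ±1.8 | ±2.5 | ±3.0 | ±3.9 |
| 5 | ±4.4 | ±6.2 | ±7.6 | ±9.8 |
| 8 | ±7.0 | ±9.9 | ±12.2 | ±15.7 |

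For example, at SD 5 and r = 0.8: 1.96 × 5 × √0.4 = 6.2.

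**5. Would the planned outputs show it?** With zero mean bias the t-test is non-significant about 95% of the time by construction, however wide the scatter. In 20,000 simulated normal data sets of 35 pairs, a non-significant t-test occurred together with a significant correlation in:

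- 95% at SD 5, r = 0.9 (limits ±4.4)
- 84% at SD 5, r = 0.5 (limits ±9.8)
- 95% at SD 8, r = 0.8 (limits ±9.9)

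**6. What escapes: a scale difference centred on the mean.** Suppose the sample mean is 8 pg/ml on both assays and the second reads 8 + 0.3 × (x − 8). A reading of 22 becomes 8 + 0.3 × 14 = 12.2, a difference of 9.8 pg/ml. The correlation is 1, the mean difference is 0 and the plot is straight. Its slope would show the difference in scale, but the stated use of the plot is only to judge linearity.

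**7. Can 35 pairs support limits of agreement?** The 95% confidence interval of each limit is about ±1.96 × √(1/35 + 1.96²/(2 × 34)) = ±0.57 SD of the differences. At SD 5 and r = 0.8 that SD is 5 × √0.4 = 3.16, so each limit is known to about ±1.8 pg/ml. That is usable.

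**The case against.** The best defence is that section 7.4 reads three outputs together and sets no rule for declaring agreement. The t-test covers bias, the plot lets a reader see scatter and slope, and the paired data are kept, so limits of agreement could be added at analysis. Much of this stands, and it rules out several stronger readings that a reader might infer.

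- **That the plan would pass assays differing by a constant or by a simple ratio.** It would not. Take a research assay reading half the clinical value with 10% noise on each, and true levels lognormal with median 6 pg/ml and log-SD 0.8. The correlation is 0.98, but the planned t-test rejects in every simulated data set.
- **That the plan will conclude the assays agree while readings differ by nearly 10 pg/ml.** No such conclusion is planned, and the size cannot be derived from the protocol. At SD 5, ±9.8 needs r near 0.5, which few would call high agreement. Women on aromatase inhibitors may also vary less than the women in section 4.1.1.
- **That Day 1 and week 4 values will be pooled, inflating r.** Section 7.4 does not say so.
- **That the safety verdict is at risk.** A primary failure needs a clinical-laboratory level above range and "at least 10 pg/ml higher than the baseline value on two consecutive collections at least four weeks apart". Research samples exist only at Day 1 and week 4, so they cannot confirm persistence. No result of the assay comparison alters the endpoint, stopping rule or sample size.

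The sentence itself still stands uncorrected. It tells the analyst to read agreement from a statistic that does not carry it, and no planned summary gives differences between paired readings in pg/ml.

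**Conclusion.** The point holds for secondary objective 2. The correlation is the wrong measure of agreement, and the t-test and linearity plot leave random scatter and mean-centred scale differences unmeasured.

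The size depends on inputs the protocol does not give. With equal assay SDs of 5 pg/ml and zero mean bias, paired readings could differ by up to about 4.4 pg/ml (r = 0.9), 6.2 (r = 0.8) or 9.8 (r = 0.5) in 95% of samples, with a t-test expected to be non-significant. With an SD of 2 pg/ml the limits at r of 0.8 to 0.9 shrink to about ±2.5 to ±1.8. The correction is worth making because it is specific and nearly free.

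**What to change.** Keep the paired t-test and the plot. Replace the sentence on correlation in section 7.4 with wording such as:

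> *Agreement will be assessed by the mean difference and 95% limits of agreement (Bland-Altman, with confidence intervals, both assays in pg/ml, on the log scale as ratios if scatter grows with level), separately for Day 1 and week 4, and by cross-classification at 10 pg/ml with percent agreement; the correlation is descriptive only.*

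Common units need stating because section 3.1 gives the research assay's sensitivity in pmol/l. With the molecular weight of 272.39 in section 4.1, 10 pg/ml is 10/0.27239 = 36.7 pmol/l. Readings too low to quantify can still enter the cross-classification, since they fall below 10 pg/ml.

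The cost is a change of protocol or SAP wording. No further samples, visits or patients are needed.
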